7.1 Inclusion Criteria

In order to be eligible for participation in this trial, the patient must:

1. Have provided written informed consent for the trial.
2. Be ≥ 18 years of age on day of signing informed consent.
3. Have at least one lesion not planned for SABR that is measurable disease based on RECIST 1.1.
4. Patients must have a histologically or cytologically confirmed metastatic non-small cell lung cancer.
5. Patients with disease previously untreated with systemic therapy must have $\geq 1\%$ PD-L1 staining and patients who have previously received systemic therapy must have $\geq 1\%$ PD-L1 staining on immunohistochemistry
6. Patients must have at least 1-3 lesions suitable for treatment with stereotactic radiotherapy.
7. Be willing to provide tissue from a newly obtained core or excisional biopsy of a tumour lesion where feasible. *Newly-obtained is defined as a specimen obtained up to 12 weeks prior to randomisation. Patients for whom newly-obtained samples cannot be provided (e.g. inaccessible or patient safety concern) may submit an archived specimen only upon agreement from the study principal investigators.*
8. Have a performance status of 0-1 on the ECOG Performance Scale (see Appendix 1).

9. Demonstrate adequate organ function as defined in table 3 below, all screening labs should be performed within 10 days of randomisation.

Table 3 Adequate Organ Function Laboratory Values

System	Laboratory Value
Haematological	
Absolute neutrophil count (ANC)	$\geq 1.5 \times 10^9 / \text{L}$
Platelets	$\geq 100 \times 10^9 / \text{L}$
Haemoglobin	$\geq 90 \text{ g/L}$ without transfusion or EPO dependency (within 7 days of assessment)
Renal	
Serum creatinine OR Measured or calculated ^a creatinine clearance (GFR can also be used in place of creatinine or CrCl)	$\leq 1.5 \times$ upper limit of normal (ULN) OR $\geq 30 \text{ mL/min}$ for patients with creatinine levels $> 1.5 \times$ institutional ULN
Hepatic	
Serum total bilirubin	$\leq 1.5 \times$ ULN OR Direct bilirubin \leq ULN for patients with total bilirubin levels $> 1.5 \text{ ULN}$
AST (SGOT) and ALT (SGPT)	$\leq 2.5 \times$ ULN OR $\leq 5 \times$ ULN for patients with liver metastases
Coagulation	
International Normalized Ratio (INR) or Prothrombin Time (PT)	$\leq 1.5 \times$ ULN unless patient is receiving anticoagulant therapy as long as PT or PTT is within therapeutic range of intended use of anticoagulants
Activated Partial Thromboplastin Time (aPTT)	$\leq 1.5 \times$ ULN unless patient is receiving anticoagulant therapy as long as PT or PTT is within therapeutic range of intended use of anticoagulants

^aCreatinine clearance should be calculated per institutional standard.

10. Life expectancy > 3 months.

11. Be willing and able to comply with all study requirements, including treatment, attending assessments and follow-up.

12. Female patient of childbearing potential should have a negative urine or serum pregnancy within 7 days of randomisation. If the urine test is positive or cannot be confirmed as negative, a serum pregnancy test will be required.

13. Female patients of childbearing potential should be willing to use 2 methods of birth control or be surgically sterile, or abstain from heterosexual activity for the course of the study through 120 days after the last dose of study medication (See Section 8.10). Patients of childbearing potential are those who have not been surgically sterilized or have not been free from menses for > 1 year.

14. Male patients should agree to use an adequate method of contraception starting with the first dose of study therapy through 120 days after the last dose of study therapy.

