8.4 Safety Follow-up – All Arms

The following assessments will be performed during the safety follow-up visit to be conducted approximately 30 days after the last dose of trial treatment or before the initiation of a new anti-cancer treatment, whichever comes first.

- Adverse events assessment: Patients with an AE of Grade > 1 will be followed until the resolution of the AE to Grade 0-1 or until the beginning of a new anti-neoplastic therapy, whichever occurs first. SAEs that occur within 30 days of the end of treatment or before initiation of a new anti-cancer treatment should also be followed and recorded.
- New anti-cancer therapy status.

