	Grade 3 or 4 that persists > 1 week	Treat with intravenous steroids followed by high dose oral steroids. When symptoms improve to Grade 1 or less, steroid taper should be started and continued over no less than 4 weeks
Type 1 diabetes mellitus		If new onset, including diabetic ketoacidosis, insulin replacement therapy is recommended
Hyperglycemia	Grade 3-4	If associated with ketosis (ketonuria) or metabolic acidosis, evaluate patients with serum glucose and a metabolic panel, urine ketones, glycosylated haemoglobin, and C-peptide. Insulin replacement therapy is recommended
Hypophysitis	Grade 2	Treat with corticosteroids. When symptoms improve to Grade 1 or less, steroid taper should be started and continued over no less than 4 weeks. Replacement of appropriate hormones may be required as the steroid dose is tapered
	Grade 3-4	Treat with an initial dose of IV corticosteroids followed by oral corticosteroids. When symptoms improve to Grade 1 or less, steroid taper should be started and continued over no less than 4 weeks. Replacement of appropriate hormones may be required as the steroid dose is tapered

Hyperthyroidism or Hypothyroidism	General	Thyroid disorders can occur at any time during treatment. Monitor patients for changes in thyroid function (at the start of treatment, periodically during treatment, and as indicated based on clinical evaluation) and for clinical signs and symptoms of thyroid disorders
	Grade 2 hyperthyroidism Grade 2-4 hypothyroidism	In hyperthyroidism, non-selective beta-blockers (e.g. propranolol) are suggested as initial therapy. In hypothyroidism, thyroid hormone replacement therapy, with levothyroxine or liothyroinine, is indicated per standard of care.
	Grade 3-4 hyperthyroidism	Treat with an initial dose of IV corticosteroid followed by oral corticosteroids. When symptoms improve to Grade 1 or less, steroid taper should be started and continued over no less than 4 weeks. Replacement of appropriate hormones may be required as the steroid dose is tapered.
Hepatic	Grade 2	Monitor liver function tests more frequently until returned to baseline values (consider weekly). Treat with IV or oral corticosteroids
	Grade 3-4	Treat with intravenous corticosteroids for 24 to 48 hours. When symptoms improve to Grade 1 or less, a steroid taper should be started and continued over no less than 4 weeks

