10.1 Pembrolizumab Dose Modifications and Delays

Adverse events associated with pembrolizumab exposure may represent an immunologic etiology. These adverse events may occur shortly after the first dose or several months after the last dose of treatment. Pembrolizumab must be withheld for drug-related toxicities and severe or life-threatening AEs as per Table 7 below. See Section 8.8 for supportive care guidelines, including use of corticosteroids. Dose reductions are not permitted.

Table 7: Dose Modification Guidelines for Drug-Related Adverse Events

General instructions: 
 1. Corticosteroid taper should be initiated upon AE improving to Grade 1 or less and continue to taper over at least 4 weeks. 2. For situations where pembrolizumab has been withheld, pembrolizumab can be resumed after AE has been reduced to Grade 1 or 0 and corticosteroid has been tapered. Pembrolizumab should be permanently discontinued if AE does not resolve within 12 weeks of last dose or corticosteroids cannot be reduced to ≤ 10 mg prednisone or equivalent per day within 12 weeks. 3. For severe and life-threatening irAEs, IV corticosteroid should be initiated first followed by oral steroid. Other immunosuppressive treatment should be initiated if irAEs cannot be controlled by corticosteroids. 				
Immune-related AEs	Toxicity grade or conditions (CTCAEv4.0)	Action taken to pembrolizumab	irAE management with corticosteroid and/or other therapies	Monitor and follow-up
Pneumonitis	Grade 2	Withhold	
 • Administer corticosteroids (initial dose of 1-2 mg/kg prednisone or equivalent) followed by taper 	
 • Monitor participants for signs and symptoms of pneumonitis • Evaluate participants with suspected pneumonitis with radiographic imaging and initiate corticosteroid treatment • Add prophylactic antibiotics for opportunistic infections
	Grade 3 or 4, or recurrent Grade 2	Permanently discontinue		

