Diarrhea / Colitis	Grade 2 or 3	Withhold	
 • Administer corticosteroids (initial dose of 1-2 mg/kg prednisone or equivalent) followed by taper 	
 • Monitor participants for signs and symptoms of enterocolitis (ie, diarrhea, abdominal pain, blood or mucus in stool with or without fever) and of bowel perforation (ie, peritoneal signs and ileus). • Participants with \geq Grade 2 diarrhea suspecting colitis should consider GI consultation and performing endoscopy to rule out colitis. • Participants with diarrhea/colitis should be advised to drink liberal quantities of clear fluids. If sufficient oral fluid intake is not feasible, fluid and electrolytes should be substituted via IV infusion.
	Grade 4	Permanently discontinue		
AST / ALT elevation or Increased bilirubin	Grade 2	Withhold	
 • Administer corticosteroids (initial dose of 0.5- 1 mg/kg prednisone or equivalent) followed by taper 	
 • Monitor with liver function tests (consider weekly or more frequently until liver enzyme value returned to baseline or is stable)
	Grade 3 or 4	Permanently discontinue		
Type 1 diabetes mellitus (T1DM) or Hyperglycemia	Newly onset T1DM or Grade 3 or 4 hyperglycemia associated with evidence of β -cell failure	Withhold	
 • Initiate insulin replacement therapy for participants with T1DM • Administer anti-hyperglycemic in participants with hyperglycemia 	
 • Monitor participants for hyperglycemia or other signs and symptoms of diabetes.
Hypophysitis	Grade 2	Withhold	
 • Administer corticosteroids and initiate hormonal replacements as clinically indicated. 	
 • Monitor for signs and symptoms of hypophysitis (including hypopituitarism and adrenal insufficiency)
	Grade 3 or 4	Withhold or permanently discontinue ¹		

Hyperthyroidism	Grade 2	Continue	
 Treat with non-selective beta-blockers (eg, propranolol) or thionamides as appropriate 	
 Monitor for signs and symptoms of thyroid disorders.
	Grade 3 or 4	Withhold or permanently discontinue ¹		

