12.9 Events of Clinical Interest

Selected non-serious and serious adverse events are also known as Events of Clinical Interest (ECI) and must be recorded as such on the Adverse Event case report forms and reported within 24 hours to the Sponsor and within 2 working days to Merck Global Safety. (Attn: Worldwide Product Safety; [contact]).

For the time period beginning at first treatment through 90 days following cessation of treatment, or 30 days following cessation of treatment if the patient initiates new anticancer therapy, whichever is earlier, any ECI, or follow up to an ECI, whether or not related to protocol treatment, must be reported within 24 hours to the Sponsor and within 24 hours to Merck Global Safety.

Events of clinical interest for this trial include:

1. an overdose of pembrolizumab, as defined in Section 12.10 Definition of an Overdose for This Protocol and Reporting of Overdose to the Sponsor, that is not associated with clinical symptoms or abnormal laboratory results.
2. an elevated AST or ALT lab value that is greater than or equal to 3X the upper limit of normal and an elevated total bilirubin lab value that is greater than or equal to 2X the upper limit of normal and, at the same time, an alkaline phosphatase lab value that is less than 2X the upper limit of normal, as determined by way of protocol-specified laboratory testing or unscheduled laboratory testing.

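### A patient admitted with liver values above Grade 1, who returns to the entry value after a Grade 2 drug-related rise, cannot meet Table 7's condition for resuming pembrolizumab

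*Combined protocol and SAP*

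**What the plan says.** **Entry (7.1, Table 3).** The general AST/ALT ceiling is 2.5 x ULN, raised to 5 x "ULN for patients with liver metastases". Total bilirubin has a ceiling of 1.5 x ULN, but a normal direct bilirubin is accepted instead "for patients with total bilirubin levels" above that, with no cap on the total.

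**Withholding and resuming (10.1, Table 7).** The table covers drug-related events. In the AST/ALT or bilirubin row, Grade 2 leads to withholding and Grade 3 or 4 to permanent discontinuation. General instruction 2 states that "pembrolizumab can be resumed after AE has been reduced to Grade 1 or 0 and corticosteroid has been tapered". Permanent discontinuation applies if the event does not resolve within 12 weeks of the last dose; *resolve* is not defined. The only relaxation of the grade condition is a note for endocrinopathies, which permits Grade 2 or lower.

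**Follow-up.** Under 8.4 a patient with an event above Grade 1 "will be followed until the resolution of the AE to Grade 0-1" or until new anti-neoplastic therapy starts, whichever is first. Under 12.8.1, a serious event still open at the end of the study or of participation can be closed when it returns to baseline.

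**Event of clinical interest (12.9).** The liver criterion is "an elevated AST or ALT lab value that is greater than or equal to 3X the upper limit of normal", with total bilirubin at least 2 x ULN and alkaline phosphatase below 2 x ULN. It applies from first treatment, whether or not related.

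**Safety analysis (14.5).** The maximum grade per patient is tabulated, for all events and for related events. Baseline grade is not used.

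**The concern.** The plan deliberately admits patients with raised liver values, then judges their recovery on an absolute grade that their entry value may already exceed. Elsewhere the protocol recognises that such patients exist: exclusion criterion 11 counts a patient as recovered from earlier treatment at Grade 1 or at baseline. The resume rule has no such wording.

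At stake is whether an eligible patient whose liver tests are back where they started can receive trial drug again, and whether the two sites would decide this alike. The answer feeds into the data, because ceasing treatment is one of the events charted under 5.3 and 14.6. For interpretation, a table of worst grades alone does not separate a patient who moved from Grade 0 to Grade 3 from one who started at Grade 2.

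**Working it through.** The plan gives no figure on this point to reproduce. The check compares thresholds and rules.

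**1. Can a patient enter above Grade 1 on AST/ALT?** Section 12.5 names CTCAE 4.03 but prints no limits, so let g be the upper limit of Grade 1 in multiples of ULN. Entry above Grade 1 is possible if the entry ceiling exceeds g.

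| Ceiling | g = 2 | g = 2.5 | g = 3 | g = 4 | g = 5 |
|---|---|---|---|---|---|
| 5 (liver metastases) | yes | yes | yes | yes | no |
| 2.5 (others) | yes | no | no | no | no |

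At the assumed g = 3, patients with liver metastases who enter above 3 and up to 5 x ULN are above Grade 1. Patients without liver metastases are not.

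**2. Bilirubin.** The alternative branch has no cap on the total, so for any Grade 1 limit some admissible value lies above it. If that limit is 1.5 x ULN (assumed), every patient admitted through this branch is above Grade 1.

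**3. The path to the conflict.** Illustration, with Grade 1 ending at 3 and Grade 2 at 5 x ULN (both assumed): entry at 4.0, a drug-related rise to 4.5, return to 4.0.
- 3 < 4.5 ≤ 5: Grade 2, so pembrolizumab is withheld.
- 4.0 > 3: back at the entry value, but still not Grade 1 or 0, so the condition in instruction 2 is not met.
- The endocrinopathy note does not apply to liver events.

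**4. What happens at 12 weeks.**
- If *resolve* means Grade 1 or 0, the patient is permanently discontinued.
- If it means return to baseline, discontinuation is not triggered, but the stated condition for resuming is still unmet. Table 7 does not say what happens next.

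**5. Follow-up of a serious event.** Suppose the event in step 3 was serious and still open when participation ends. At 4.0 x ULN, 12.8.1 allows closure because baseline is reached. Section 8.4 does not, unless new anti-neoplastic therapy has started.

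**6. Event of clinical interest.** This step needs no CTCAE limit. Take AST 4 x ULN with liver metastases, total bilirubin 2.5 x ULN and normal direct bilirubin.
- Entry: 4 ≤ 5, and 2.5 > 1.5 is accepted through the direct bilirubin branch. Table 3 has no alkaline phosphatase criterion.
- Section 12.9: 4 ≥ 3 and 2.5 ≥ 2. With alkaline phosphatase below 2 x ULN, the criterion is met without any change from entry.

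**7. Weight of one patient.** With 16 per arm, 1/16 = 6.25 percentage points of an arm's toxicity rate.

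**The case against.** The strongest reply is that instruction 2 concerns a drug-related event, whereas a value present before treatment is recorded as a baseline abnormality (footnote 4 to Tables 1 and 2). A rise that has returned to the entry value can then be seen as a finished event. That is a sensible reading, but the protocol does not state it, and instruction 2 names a grade where exclusion criterion 11 adds baseline.

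Several stronger readings are tempting and are not supported:

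- *That the patient must be discontinued.* This depends on the undefined word in step 4.
- *That the protocol defines recovery as return to baseline and contradicts itself directly.* Table 4 says "Monitor liver function tests more frequently until returned to baseline values", and Table 7 says to monitor "until liver enzyme value returned to baseline or is stable". Both set how long to test more often; neither permits re-dosing.
- *That follow-up under 8.4 can never end.* It also ends at new anti-neoplastic therapy.
- *That small fluctuations enter the primary endpoint as grade 3 or higher.* A laboratory value is an event only if the investigator judges it clinically significant (12.7), and the primary endpoint counts related events only (5.3). From 4.5 x ULN, a rise of 5/4.5 - 1 = 11% does reach the assumed Grade 3 limit. But Table 7 discontinues every patient with a drug-related Grade 3 liver event, so that figure does not measure the resume conflict.
- *That the kidney exception in Table 3 has the same problem.* The renal row of Table 7 concerns nephritis and renal dysfunction and is not tied to a creatinine limit.

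The 12.9 criterion is a reporting trigger. Meeting it at entry values alters neither dosing nor grade, and the combination in step 6 is probably rare.

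**Conclusion.** The mismatch stands for liver values. As written, a patient admitted above Grade 1 whose drug-related rise is managed as Grade 2 and returns to the entry value cannot meet the condition for resuming. For AST/ALT this holds for any Grade 1 limit below 5 x ULN; the value of 3 x ULN is an assumption. The differing endpoints in 8.4 and 12.8.1 affect the same patients, and the overlap of 12.9 with the entry limits follows from printed figures alone.

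The documents do not say how many patients would enter under these exceptions. If the number were 0 to 3 of 32, an assumption without a source, that would be 0 to 3/32 = 9.4% of the trial, and only those with a Grade 2 drug-related liver event would meet the resume conflict. The sample size, the tests and the review trigger in 14.10, which counts only pneumonitis and colitis, are unaffected. It is worth correcting because a stated rule has an apparently unintended result for patients whom the plan chose to admit.

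**What to change.** The sponsor's clinicians should reconcile Table 3 with Table 7 instruction 2, 8.4, 12.8.1 and 12.9. They should state one recovery reference for patients admitted above Grade 1, and say what *resolve* means in the 12-week rule. Which reference to use is a clinical decision on which this review takes no position.

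In 14.5, add a table of baseline grade by worst grade for hepatic laboratory toxicity, by arm and overall. Mark the grade 3 or higher events in patients who entered above Grade 1.

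The cost is a wording amendment in a few places and one extra table. The screening liver tests, the recorded baseline abnormalities and the tests at each cycle already supply the data.

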7.2 Exclusion Criteria

The patient must be excluded from participating in the trial if the patient:

1. Has had previous high dose radiotherapy (biological equivalent of >30Gy in 10#) to an area to be treated which includes vertebral bodies (see below).

Note: Previous high dose radiotherapy is defined as a biological equivalent dose to above that of 30 Gy in 10 fractions using an alpha/beta ratio (50) of 3. Where a patient has received radiotherapy to an equivalent or lower dose than defined above, stereotactic radiotherapy of the area may be considered. In doing so, assessment of the volume and total dose received by any overlap region must be made, and documented by generating a cumulative plan incorporating both the previous and current treatment fields. It is the treating radiation oncologist's responsibility to review both the current plan and the cumulative plan inclusive of previous radiotherapy.

2. Has had previous thoracic radiotherapy of > 36Gy within the 6 months prior to randomisation.
3. Has known active central nervous system (CNS) metastases and/or carcinomatous meningitis. Patients with small asymptomatic or previously treated brain metastases may participate provided they are stable (without evidence of progression by imaging for at least four weeks prior to the first dose of trial treatment and any neurologic symptoms have returned to baseline), have no evidence of enlarging brain metastases, and are not using steroids for intracranial neurological symptoms at least 7 days prior to trial randomisation. This exception does not include leptomeningeal disease which is excluded regardless of clinical stability.
4. Has evidence of Spinal Cord Compression.
5. Has a Spinal Instability Neoplastic Score ≥ 7 unless lesion reviewed by a neurosurgical service and considered stable (see Appendix 2).
6. Requires surgical fixation of bone lesion for stability. All surgical fixation and instrumentation must be completed before randomisation on study.
7. Is currently participating and receiving study therapy or has participated in a study of an investigational agent and received study therapy or used an investigational device within 4 weeks of randomisation.
8. Has a diagnosis of immunodeficiency.
9. Has a known history of active TB (Bacillus Tuberculosis)
10. Has a hypersensitivity to pembrolizumab or any of its excipients.
11. Has had a prior anti-cancer monoclonal antibody (mAb) within 4 weeks prior to randomisation or who has not recovered (i.e., \leq Grade 1 or at baseline) from adverse events due to agents administered more than 4 weeks earlier.
12. Has diagnosed and/or treated additional malignancy within 5 years prior to randomisation with the exception of: curatively treated basal cell carcinoma of the skin, squamous cell carcinoma of the skin, curatively treated early stage cervical

cancer, breast cancer or prostate cancer with no evidence of active disease. Other exceptions may be considered following consultation with the principal investigator

13. Has active autoimmune disease that has required systemic treatment in the past 2 years (i.e. with use of disease modifying agents, corticosteroids or immunosuppressive drugs). Replacement therapy (e.g. thyroxine, insulin, or physiologic corticosteroid replacement therapy for adrenal or pituitary insufficiency, etc.) is not considered a form of systemic treatment.
14. Has a history of (non-infectious) pneumonitis that required steroids or current pneumonitis.
15. Has had any systemic anti-cancer therapy or radiation therapy within 4 weeks prior to randomisation
16. Has known interstitial lung disease
17. Has an active infection requiring systemic therapy.
18. Has a history or current evidence of any condition, therapy, or laboratory abnormality that might confound the results of the trial, interfere with the patient's participation for the full duration of the trial, or is not in the best interest of the patient to participate, in the opinion of the treating investigator.
19. Has known psychiatric or substance abuse disorders that would interfere with cooperation with the requirements of the trial.
20. Has received prior therapy with an anti-PD-1, anti-PD-L1, or anti-PD-L2 agent.
21. Has a known history of Human Immunodeficiency Virus (HIV) (HIV 1/2 antibodies).
22. Has known active Hepatitis B (e.g., HBsAg reactive) or Hepatitis C (e.g., HCV RNA [qualitative] is detected).
23. Has received a live vaccine within 30 days of randomisation.

Note: Seasonal influenza vaccines for injection are generally inactivated flu vaccines and are allowed; however intranasal influenza vaccines (e.g., Flu-Mist®) are live attenuated vaccines, and are not allowed.

